13.3 Publication Policy

All information concerning Zosano Pharma operations, patent applications, formulas, manufacturing processes, and basic scientific data provided by Zosano Pharma to the investigator and not previously publishes, are considered confidential and remain the sole property of Zosano Pharma.

It is understood by the investigator that Zosano Pharma will use the information obtained in this clinical study in connection with C213, and therefore may disclose this information as required to other Zosano investigators, appropriate international regulatory agencies, or others. In agreeing to participate in this study, the investigator understands that he/she has an obligation to provide complete test results and all data developed during this study to Zosano Pharma. Zosano Pharma requires that permission to publish details of this study must be obtained in writing by Zosano as further detailed in the Clinical Study Agreement signed by the investigator and/or institution.

13.4 Retention of Records

The Investigator must maintain adequate records for the study including completed eCRFs, medical records, laboratory reports, signed ICFs, drug disposition records, adverse event reports, information regarding subjects who discontinued, all correspondence with the IRB/IEC and the Sponsor (or designee) and other pertinent data.

All records are to be retained by the Investigator as required by applicable law or regulation.

To avoid any possible errors, the Investigator must contact Zosano (or designee) prior to the destruction of any study records. The Investigator will also notify Zosano (or designee) in the event of accidental loss or destruction of any study records.

APPENDIX 1 INVESTIGATOR ASSESSMENTS – RATING FOR BRUISING, ERYTHEMA, EDEMA AND PHOTOGRAPHS

The Bruising, Erythema, and Edema assessment will be performed by the investigator at the final visit 3 (or early discontinuation). Any findings with an intensity rating of 1 (Mild intensity), 2 (Moderate intensity), or 3 (Severe intensity) must be recorded as an adverse event in the eCRF and followed to resolution. The investigator will use the definitions of AE Severity Ratings for Mild, Moderate, Severe, Life-Threatening (Section 8.2.1.3) to assess the Severity of the AE.

Symptom	Intensity Rating (circle)
Bruising spots	0 = Clear
where C213 was applied?	1 = Mild intensity
	2 = Moderate intensity
	3 = Severe intensity

Symptom	Intensity Rating (circle)
Skin Erythema	0 = Clear
where C213 was applied?	1 = Mild intensity
	2 = Moderate intensity
	3 = Severe intensity

Symptom	Intensity Rating (circle)
Skin Edema where	0 = Clear
C213 was applied?	1 = Mild intensity
	2 = Moderate intensity
	3 = Severe intensity

The photographs below for bruising, erythema, and edema are intensity examples for the investigator as to what these skin reaction(s) in the upper arm region may look like. The investigator will use the definitions of AE Severity Ratings for Mild, Moderate, Severe, Life-Threatening (Section 8.2.1.3) to assess the Severity of the AE.

Intensity Ratings

Bruising

Mild

Moderate

Severe

Erythema

None (Clear)

Mild

Moderate

Severe

[figure not shown]
Edema

[figure not shown]
None (Clear)

Mild

Moderate

Severe

APPENDIX 2 SAMPLE SUBJECT eDIARY QUESTIONS

Qualifying Cluster Headache Double-Blind Period (eDiary is Activated at Visit 2)

- Are you having a cluster headache now? (Yes, No)
- How bad is your headache pain? (Mild, Moderate, Severe)
- Are you experiencing any of the following (please scroll down and select all that apply)?

Feeling Restless/Agitated? (Yes, No)

Eye redness or tearing on the same side as pain? (Yes, No)

Runny or stuffy nose on the same side as pain? (Yes, No)

Swollen eyelid on the same side as pain? (Yes, No)

Forehead and face sweating on the same side as pain? (Yes, No)

Drooping of the upper eye lid, or pupil getting smaller on same side as pain? (Yes, No)

None of the above (Yes, No)

- Did you treat your cluster headache with a triptan or ergot in the past 24 hours?
- If a non-qualifying headache:

The following text shows - **DO NOT** APPLY THE PATCHES. YOU **HAVE NOT** REPORTED a qualifying cluster headache. Please save your answers and return to the diary next time you think you are experiencing a headache.

• *If a qualifying headache:*

The following text shows - You have reported a qualifying headache. Please apply the first patch now. After applying the first patch, please respond to the question below:

Have you applied your first patch? (Yes, No)

Please apply the second patch now.

Post Patches Application Questions at: 30 min

- Where were the study drug patches applied? (Both to left arm, Both to right arm, One patch to each arm, One patch to left arm, One patch to right arm)
- Please remove the patches from your upper arm, fold in half, and discard. Press the next button once you have removed both patches.

• *Reminder* Text – You have 1 post treatment questionnaire left to complete. Please do not turn off your device. You may press next to complete this questionnaire.

Post Patches Application Questions/text at: 5, 10, 15, 20, 30, 60 min

- How bad is your headache pain? (None, Mild, Moderate, Severe)
- Did you take any medication, since your last diary entry, other than the patches you applied to treat your headache? (Yes, No)
- Do you feel able to perform your usual daily activities? (Yes/No)
- Your next assessment is due at [time]. Please keep your device with you. (at 5, 10, 15, 20, 30 minute)
- Thank you. You have answered all study related questions and your physician will contact you about setting up your final visit (at 60 minutes only)

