3.2.2 Inclusion Criteria

Inclusion Criteria:

Subjects presenting with all of the following may be included in the study:

- 1. Able to provide written informed consent
- 2. Women or men 18 to 65 years of age
- 3. Greater than 1-year history of episodic or chronic cluster headache with onset prior to 50 years of age. Diagnosis must comply with ICHD-3 (International Headache Society (IHS) diagnostic criteria. Diagnostic criteria must include a history of at least 5 attacks not attributed to any other disorder that include all of the following criteria:
 - a) Severe or very severe unilateral orbital, supraorbital and/or temporal pain lasting 45-180 minutes (average, when untreated)
 - b) Either or both of the following:
 - 1. At least one of the following symptoms or signs, ipsilateral to the pain:
 - (a) Conjunctival injection and/or lacrimation
 - (b) Nasal congestion and/or rhinorrhea
 - (c) Eyelid edema
 - (d) Forehead and facial sweating
 - (e) Miosis and or/ptosis
 - 2. A sense of restlessness or agitation
 - c) Attacks have a frequency between one every other day and eight per day for more than half of the time when the disorder is active
 - d) Not better accounted for by another ICHD diagnosis
- 4. Cluster history during the 12-month period prior to the screening visit must include:
 - a) at least 1 cluster period
 - b) averaging 2-6 headaches per day
 - c) lasting at least 7 days
- 5. Subject can distinguish cluster headaches from other headaches (i.e., migraine and tension-type headaches)

- 6. Women of child-bearing potential must not be pregnant, must agree to avoid pregnancy during the trial, and must use one of the following or be surgically sterile: intrauterine device or a hormonal contraceptive
- 7. Able to understand the operation of the electronic diary and able to apply the demo study drug patch correctly.

3.2.3 Exclusion Criteria:

Subjects presenting with any of the following will not be included in the study:

- 1. Contraindication to triptans
- 2. Use of any prohibited concomitant medications within 7 days prior to screening (See Table 6 Prohibited Concomitant Medications)
- 3. History of hemiplegic migraine or migraine with brainstem aura
- 4. Participation in another investigational trial within 30 days or 5 half-lives of investigational product (whichever is longer)
- 5. Previous M207/C213 exposure in a clinical trial

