- 6. Subject has other significant pain problems that might confound the study assessments in the opinion of the Investigator.
- 7. Diagnosis of any malignant disease (other than adequately treated or excised non-metastatic basal cell carcinoma or squamous cell carcinoma of the skin) within the 5 years prior to screening
- 8. History of unstable psychiatric illness requiring medication or hospitalization in the 12 months prior to study screening
- 9. Subjects who have a known allergy or sensitivity to zolmitriptan or its derivatives or formulations
- 10. Subjects who have known allergy or sensitivity to adhesives
- 11. Subjects who have skin lesions or tattoos covering the entire potential area(s) of C213 application
- 12. Women who are pregnant, breast-feeding or plan a pregnancy during this study
- 13. Clinically significant liver disease (ALT > 150 U/L; AST > 130 U/L or bilirubin > 2x ULN)
- 14. Clinically significant kidney disease (eGFR < 60 ml/min /1.73 m² or to creatinine > 1.5 x ULN)
- 15. Subject has clinically significant ECG findings, defined by:
 - a) ischemic changes (defined as > 1mm of down-sloping ST segment depression in at least two contiguous leads)
 - b) Q-waves in at least two contiguous leads

- c) clinically significant intra-ventricular conduction abnormalities (left bundle branch block or Wolf-Parkinson-White syndrome)
- d) clinically significant arrhythmias (e.g., current atrial fibrillation)
- 16. History of coronary artery disease (CAD), coronary vasospasm (including Prinzmetal's angina), aortic aneurysm, peripheral vascular disease or other ischemic diseases (e.g., ischemic bowel syndrome or Raynaud's syndrome)
- 17. Three or more of the following CAD risk factors:
 - a) Current tobacco use
 - b) Hypertension (systolic BP > 140 or diastolic BP > 90) or receiving anti-hypertensive medication for treatment of hypertension
 - c) Hyperlipidemia LDL > 159 mg/dL and/or HDL < 40 mg/dL (or on prescribed anti-cholesterol treatment)
 - d) Family history of premature coronary artery disease (CAD) (< 55 years of age in male first-degree relatives or < 65 years of age in female first degree relatives)
 - e) Diabetes mellitus
- 18. History of cerebral vascular accident (CVA), transient ischemic attacks (TIA), or seizures
- 19. History of concurrent illness that requires hospitalization within 30 days prior to study screening
- 20. Any other household member currently participating in a C213 study or relative of site staff member

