4.3 Dose, Dose Schedule, and Route of Administration

The study drug will be dispensed only to qualified, randomized subjects included in this study in accordance with the eligibility criteria specified in the study protocol.

When a subject experiences a qualifying headache (as confirmed by answering questions in the eDiary), the subject will self-administer the study drug. Subjects will be trained on how to administer the patches using the C213 applicator supplied in the kit.

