6.1.3.1 Day 1 through Week 48: Treatment of a Qualifying Cluster Headache

The following constitutes a cluster headache that qualifies for treatment with study drug:

- Severe unilateral orbital, supraorbital and/or temporal pain
- Either or both of the following:
 - 1) at least one of the following symptoms or signs, ipsilateral to the pain:
 - conjunctival injection and/or lacrimation
 - nasal congestion and/or rhinorrhea
 - evelid edema
 - forehead and facial sweating
 - miosis and/or ptosis
 - 2) a sense of restlessness or agitation

The following procedures are to be performed by the subject for a cluster headache from Day 1 through 48 weeks of the double-blind period:

• Using the eDiary, the subject will record the following to confirm the headache meets the qualifications for a cluster headache:

Cluster headache symptoms and pain assessment

- Once the qualifying cluster headache has been confirmed, subject self-administers the study drug patches. Subjects will apply two patches to the upper arm.
- Subject will continue to record the following in the eDiary, post self-administration of the patches at 5 min, 10 min, 15 min, 20 min, 30 min and 60 mins.

Cluster headache symptoms, pain assessment, and whether rescue therapy was needed

- For the cluster headache to be qualifying for study medication, no triptans or ergots are allowed within 24 hours prior to onset of cluster headache. If rescue therapy is required by the subject, rescue therapy other than a triptan or ergot is permitted at or after 20 minutes post study drug administration.
- Subject will contact the site to schedule a Visit 3 follow-up visit within 1-8 days of study drug treatment following administration of study drug.

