6.2.10 Previous, Concomitant and Prohibited Medications

Concomitant medications will be recorded on the appropriate source document and on the appropriate eCRF at all visits including screening, randomization day, and end of study (or early discontinuation). All previous and concomitant medications taken within 90 days prior to the screening visit must be recorded in the source document and eCRF. When new medications are started and come to the attention of the investigator between scheduled visits, they will be recorded that day on the appropriate source document and on the appropriate eCRF.

No triptans or ergots are allowed within 24 hours prior to onset of current cluster headache symptoms. If rescue therapy is required by the subject, rescue therapy other than a triptan or ergot is permitted at or after 20 minutes post study drug administration. Ergots and triptans may be resumed 24 hours after dosing with study medication.

No lotions, ointments or powders applied to the skin immediately before (within an hour) or for 24 hours after applying the patches are allowed.

Table 6 lists all prohibited medications. Medications listed in Table 6 are prohibited from 7 days prior to screening through the final visit.

Table 6: Prohibited Concomitant Medications

Drug Type	Medication
Prescription anticoagulants	Entire class
Monoamine oxidase inhibitors	Entire class
Potent CYP450 3A4 Inhibitors	Ketoconazole
	Erythromycin
	Clarithromycin
	Cimetidine
	Grapefruit
CYP450 1A2 Inhibitors/Inducers	Ciprofloxacin

Drug Type	Medication
	Enoxacin
	Fluvoxamine
	Alpha-Naphthoflavone
	Furafylline
	Omeprazole (OTC)
	Lansoprazole (OTC)
	Fluvoxamine
	Enoxacin
	Phenytoin
	Rifampin
	Ritonavir
	teriflunomide
	Methoxsalen
	Mexiletine
	Tobacco Cigarettes

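### The sample pre-dose diary question asks only about treating the cluster headache, so a triptan or ergot taken for migraine can pass although the protocol bars any within 24 hours

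*Protocol*

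**What the plan says.** Protocol 6.1.3.1 sets the rule as a condition of treatment: "For the cluster headache to be qualifying for study medication, no triptans or ergots are allowed within 24 hours prior to onset" of the headache. Section 6.2.10 repeats it: "No triptans or ergots are allowed within 24 hours prior to onset of current cluster headache symptoms". Neither limits the rule by the reason the drug was taken. Section 3.2.5 words the restriction differently: it bars anything taken for the subject's headache symptoms in the same window.

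The decision to dose is made at home through the diary. Section 4.3 says: "When a subject experiences a qualifying headache (as confirmed by answering questions in the eDiary), the subject will self-administer the study drug". Section 6.1.3 says the same.

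Appendix 2 prints the sample diary. Its one pre-dose medication item is "Did you treat your cluster headache with a triptan or ergot in the past 24 hours". A subject who passes sees "You have reported a qualifying headache" and is instructed to put on the first patch.

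On migraine, inclusion criterion 5 (section 3.2.2) requires: "Subject can distinguish cluster headaches from other headaches (i.e., migraine and tension-type headaches"). Exclusion criterion 3 (section 3.2.3) removes only "History of hemiplegic migraine or migraine with brainstem aura".

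**The concern.** The diary item is narrower than the rule it should enforce. The rule concerns any exposure to a triptan or ergot; the item concerns only exposure taken to treat a cluster headache. A subject with ordinary migraine can enrol, and inclusion 5 selects for people who can tell the two headaches apart. Such a subject, having taken a triptan for migraine that morning, can honestly answer no to the printed question and be told to apply the patches.

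What is at stake is patient safety. The protocol keeps study drug apart from other triptans and ergots on both sides of dosing: 24 hours before onset, and 24 hours after dosing, when they are also barred as rescue (6.2.10). The printed item can let through the co-exposure that these rules are meant to prevent. The documents show no effect on the efficacy comparison, and none is claimed.

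**Working it through.** No figure in the plan bears on this point, and rewording the item changes no sample size, alpha level or power. The check is a comparison of texts.

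**1. Scope of the rule against scope of the question**

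| Place | Drugs covered | Reason for use | Window counted back from |
|---|---|---|---|
| Protocol 6.1.3.1 | Triptans, ergots | Any | Headache onset |
| Protocol 6.2.10 | Triptans, ergots | Any | Onset of current symptoms |
| Protocol 3.2.5 | Any medication | Headache symptoms | Onset of current symptoms |
| Appendix 2 item | Triptans, ergots | Treating the cluster headache | Diary entry |

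The diary item has the narrowest reason for use of the four. Section 3.2.5 does not rescue it, because a triptan taken for migraine is naturally a drug taken for headache symptoms. The different starting point of the window is a small further mismatch.

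**2. Is there another medication screen before dosing?** Appendix 2 lists four questions before the qualifying screen: cluster headache now, pain level, accompanying symptoms, and triptan or ergot use. One of the four concerns medication, and it is the item at issue.

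**3. Can an eligible subject be in this position?** Yes. Only two migraine types are excluded. Triptans and ergots are not listed in Table 6, so before dosing only the 24-hour rule governs their timing. Section 6.2.10 allows them to be resumed 24 hours after dosing, so the sponsor expects some subjects to use them.

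**4. Does another control act at the moment of dosing?**
- Visit 2 reviews the definition of a qualifying headache (6.1.2), but dosing may follow up to 48 weeks later.
- Site calls every 4 weeks cover concomitant medication and diary reminders (6.1.5), against a 24-hour window.
- Exclusion 6 turns on the investigator's opinion: "Subject has other significant pain problems that might confound the study assessments in the opinion of the Investigator". It does not address triptan timing.
- The call within 2 days of dosing (6.1.6), the Visit 3 medication record (6.1.7) and the blinded deviation review (SAP 8.2) all come after exposure.

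None of these screens at dosing.

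**5. Size.** Under 1:1:1 allocation, 2 of 3 arms contain zolmitriptan, and each subject treats one attack (SAP 3). The documents give no rate of comorbid migraine or of triptan use for it, so no frequency can be computed.

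**The case against.** The strongest reply is that this is a wording point on an illustrative form. Appendix 2 is headed as a sample, and this item prints no response options or branching rule. The deployed diary, its training module and the reminder card (SAP 3.4) are not in the documents. Section 6.1.3.1 lists only symptoms and pain as what the subject records to confirm the headache and states the medication rule separately, so the diary need not be its only enforcement. Subjects are taught the definition at Visit 2. The scenario also needs several things together: migraine, a triptan or ergot taken for it within 24 hours of the one treated attack, and a literal reading despite training. No hazard is quantified, and section 1.2 reports that oral zolmitriptan was tolerated at doses well above 3.8 mg.

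Much of this stands as a limit on size and certainty: the deployed text may differ, the frequency is probably low, and the harm is not quantified. It does not remove the mismatch. If the printed item was used, it admits an attack that 6.1.3.1 disqualifies, and sections 4.3 and 6.1.3 let the diary result release the dose. Training may prevent the error, but it is not a check at dosing. The tolerability data concern zolmitriptan itself and do not address use alongside an ergot or a second triptan.

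**Conclusion.** The concern holds. As printed, the pre-dose item is narrower than the 24-hour rule in 6.1.3.1 and 6.2.10, and an eligible subject could answer it truthfully and still breach the rule. The consequence is possible self-application of zolmitriptan, in two of three arms, within 24 hours of another triptan or an ergot, detected only afterwards. This is a low-priority safety point, worth acting on because the remedy is cheap. It rests on two assumptions that the documents cannot settle: that the deployed diary used the sample wording, and that some subjects treat migraine with these drugs. It changes no endpoint, population or test.

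**What to change.** Reword the item as *Have you taken any triptan or ergot, for any reason, in the past 24 hours? (Yes, No)*, with a yes leading to the existing screen that tells the subject not to apply the patches. First settle which 24-hour rule governs. If it is 6.1.3.1 and 6.2.10, this wording fits; if it is 3.2.5, the item must ask about any headache medicine. The starting point of the window (onset or diary entry) can be aligned in the same edit.

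SAP section 12 already refers to the actual number randomized, so dosing may be over. In that case, check the wording that was deployed and review the Visit 3 medication records for triptan or ergot use in the window. If the sample wording was used, a diary answer of no cannot by itself show compliance with 6.1.3.1.

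The cost is one reworded item, or one check of the deployed wording and of records already collected. The only downside of rewording is that a few attacks are turned away, and the protocol already disqualifies those.

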# **DOCUMENT HISTORY**

Version	Date	Author	Description
1.0	14APR2021	[name]	Final Version

## Final Version 1.0

# **ABBREVIATIONS**

ABBREVIATION	DEFINITION OR DESCRIPTION
AE	Adverse Event
ADaM	Analysis Data Model
BMI	Body Mass Index
CI	Confidence Interval
CMH	Cochran Mantel Haenszel
CRF	Case Report Form
CRO	Contract Research Organization
CSR	Clinical Study Report
ECG	Electrocardiogram
EDC	Electronic Data Capture
eDiary	Electronic Diary
e.g.	Exempli gratia (for example)
EMA	European Medicines Agency
ET	Early Termination
FDA	Food and Drug Administration
ICH	International Council for Harmonization
i.e.	id est (that is)
MedDRA	Medical Dictionary for Regulatory Activities
mITT	Modified Intent-to-Treat
N, n	Number (of subjects)
SAE	Serious Adverse Event
SAP	Statistical Analysis Plan
$SAS^{ ext{ ext{ ext{$\mathbb{R}}}}}$	Statistical Analysis System
SD	Standard deviation
SDTM	Study Data Tabulation Model
SE	Standard Error
SOC	System Organ Class
TEAE	Treatment Emergent Adverse Event

Protocol: CP-2019-001 Page 7 of 26

Final Version 1.0

#### 1. OVERVIEW

This Statistical Analysis Plan (SAP) describes the planned analysis and reporting for protocol CP-2019-001: A randomized, double-blind, multi-center, parallel-group comparison of the efficacy and safety of the C213 (Zolmitriptan Microneedle System) to placebo for the acute treatment of cluster headaches, dated 27 June 2019, Amendment 1, dated 16 July 2019, Amendment 2, dated 01 October 2019 and Amendment 3, dated 15 April 2020.

The structure and content of this SAP provides sufficient detail to meet the requirements identified by FDA, European Medicines Agency (EMA), and International Council for Harmonization (ICH) of Technical Requirements for Registration of Pharmaceuticals for Human Use: Guidance on Statistical Principles in Clinical Trials.

The planned analyses identified in this SAP may be included in clinical study reports (CSRs), regulatory submissions, or future manuscripts. Also, post-hoc exploratory analyses not necessarily identified in this SAP may be performed to further examine study data. Any post-hoc, or unplanned exploratory analysis performed will be clearly identified as such in the final CSR.

In preparation of this SAP, the following documents were reviewed and considered in addition to the literature references cited in this SAP:

- Clinical Research Protocol CP-2019-001 Final v1.0 issued 27 June 2019, Amendment 1, dated 16 July 2019, Amendment 2, dated 01 October 2019 and Amendment 3, dated 15 April 2020.
- Case report forms (CRFs) for Protocol CP-2019-001
- ICH Guidance on Statistical Principles for Clinical Trials (E9)
- FDA response to meeting request dated 07 February 2019

Per FDA request, Amendment 3 incorporated changing time zero from the time of the second patch application to be the time of the first patch application, so that the primary efficacy endpoint would be measured at 15 minutes from the start of dosing.

The reader of this SAP is encouraged to also read the clinical protocol, and other identified documents, for details on the planned conduct of this study.

